#### 4.1.1. Sample Size Determination

There was no formal sample size calculation for Part 1. Six patients in each cohort will provide sufficient data to evaluate safety and a preliminary assessment of changes in muscle volume and muscle strength.

The sample size calculation for Part 2 is based upon the percent change from baseline in total muscle volume of the injected TA muscle 3 weeks after the last dose. A 10% difference between ACE-083-treated and placebo groups in the percent change in total muscle volume from baseline is considered to be clinically meaningful. The standard deviation (SD) is assumed to be approximately 9% for each group, based on preliminary MRI data for the ACE-083-treated side from the initial TA cohort in Part 1. Similar assumptions apply for the treatment of the BB muscle.

Assuming a 2-sided type I error rate of 0.10, a 10% difference in percent change from baseline between ACE-083-treated and placebo groups in total muscle volume, a standard deviation of 9% for each group, and a 1:1 randomization, 83% power is achieved with a total sample size of 24 for the TA muscle (12 active, 12 placebo), based on a standard t-test.

In addition, this sample size also provides 83% power to detect a 10% difference in 6-minute walk test distance, based on a similar estimated SD of 9% and a 2-sided type 1 error rate of 0.10.

In order to account for dropouts (up to 15%), 28 patients will be randomized to study treatment for each muscle (14 active, 14 placebo) to ensure that at least 12 patients per treatment group complete the double-blind treatment period.

#### 4.1.2. Computing Environment

The analysis of clinical data from both Parts 1 and 2 will be performed under the direction of the Acceleron Pharma Biostatistics Department, using SAS® (version 9.4 or higher) and R.

#### 4.1.3. Treatment Description

Treatment descriptions as well as abbreviations used in tables, listings, and figures are described below:

##### Part 1

Unless otherwise stated, tables and figures will be presented as shown below:

Part 1 – Tibialis Anterior

ACE-083 150 mg Unilateral	ACE-083 200 mg Unilateral	ACE-083 200 mg Bilateral	Overall
------------------------------	------------------------------	-----------------------------	---------

## Part 1 – Biceps Brachii

ACE-083 150 mg Unilateral	ACE-083 200 mg Unilateral	ACE-083 240 mg Unilateral	Overall
------------------------------	------------------------------	------------------------------	---------

Listings will contain only the treatment groups shown with no “Overall” group.

**Part 2**

Unless otherwise stated, tables and figures will be presented using one or more of the following as shown below, depending on what is being summarized/analyzed.

## Part 2 – Double-blind period

Tibialis Anterior			Biceps Brachii		
Placebo	ACE-083	Overall	Placebo	ACE-083	Overall

## Part 2 – Open-label period – by treatment group sequence

Tibialis Anterior		Biceps Brachii	
ACE-083→ACE-083	Placebo→ACE-083	ACE-083→ACE-083	Placebo→ACE-083

## Part 2 – Open-label period – Pooled across treatment group sequence

Tibialis Anterior	Biceps Brachii
ACE-083	ACE-083

Listings will contain the treatment groups shown above however, there will be no “Overall” group.

**4.1.4. Definitions of Baseline****Part 1 and Part 2 (Double-blind phase)**

For MRI, PD, and safety data, baseline is defined as the last non-missing assessment prior to the first dose of study drug administration. Theoretically, this is the Day 1 pre-dose assessment. For patients that are randomized (applicable to patients participating in Part 2) but do not receive any study drug administration, the date of randomization will be the baseline reference.

For motor function data (lower leg and upper arm functional assessments), strength (QMT by handheld device), gait, and FSHD-HI data whose pre-treatment assessments are performed up to three times prior to the first dose, the baseline is defined as the average of the non-missing values. Theoretically, this would be at the Screening Day -28, Screening Day -7, and Day 1 visits. The first dose date will serve as the reference from which the non-missing pre-treatment values would be identified. For patients that are randomized (applicable to patients participating in Part 2) but do not receive any study drug administration, the date of randomization will be the baseline reference. The last non-missing assessment prior to the first dose of study drug administration will also be determined for this data and will be available for sensitivity analyses for any analyses of changes from baseline as appropriate.

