Per Protocol Set: All patients enrolled/randomized in the study, who have received at least one dose of study drug (including placebo) with no major protocol violations and at least one post-baseline efficacy evaluation

Pharmacokinetics Population: All patients who have received at least one dose of study drug and have sufficient PK samples collected and assayed for PK analysis

Statistical Analysis:

Complete details regarding the statistical analyses outlined below will be presented in a separate statistical analysis plan. For statistical analyses involving safety data, these will be done on the safety population. For statistical analyses involving pharmacokinetic data, these will be done on the pharmacokinetics population. For statistical analyses involving efficacy and/or pharmacodynamics data, these will be done using the full analysis set and per protocol set populations.

Part 1: Safety, pharmacodynamic and efficacy data will be summarized by cohort. For each efficacy parameter, the absolute and percent change from baseline in the injected TA or BB and, with the exception of motor function tests and FSHD-HI total score and subscale score data, the raw and percent change from baseline of the treated, untreated, and treated minus untreated TA or BB muscle will be presented over time for patients receiving unilateral dosing of ACE-083.

For efficacy measurements that are collected multiple times during the 1-month screening period, changes observed during this time will serve as the control for each patient. They will be summarized together with post-baseline data.

Part 2: The primary efficacy parameter will be the percent change in total muscle volume from baseline of the injected TA or BB 3 weeks after the last dose of the double-blind treatment period. A repeated measures analysis of covariance model will be used to compare the two treatment groups (ACE-083 and placebo) using a 2-sided 0.10 significance level. If the 3-week post last dose data from the double-blind treatment visit are missing, the last observation will be carried forward. Additional techniques for handling missing data will also be evaluated as sensitivity analyses to the last observation carried forward approach.

Other strength and functional measurements will be tested similarly. Estimates of the effect of ACE-083 and corresponding 90% confidence intervals will be produced.

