14.2.3. Efficacy Data

14.2.3.1. Part 1

MRI

MRI variables will include total muscle volume (TMV) [mm³], intramuscular fat fraction (FF) [%] and other calculated volume and mass parameters.

Muscle strength

- (For TA muscle): Ankle dorsiflexion peak force value which is the maximum of three measurements from the hand-held dynamometer or fixed system,
- (For BB muscle): Elbow flexion peak force value which is the maximum of three measurements from the hand-held dynamometer or fixed system

For each parameter in unilateral cohorts, the raw data as well as the absolute and percent change from baseline in the treated TA or BB muscle, untreated TA or BB muscle, and the treated minus untreated TA or BB muscle will be summarized for each scheduled time point. For dose cohorts where the administration is bilateral, descriptive statistics of raw data, absolute and percent change from baseline will be provided by side treated [right and left] as well as the mean of the right and left sides for MRI and muscle strength parameters.

Baseline is defined as the last non-missing value prior to first dose of ACE-083. Theoretically, this should be the Day 1 pre-dose value. Such summaries will also be done for raw data and change from baseline for each primary efficacy parameter.

Estimates of the effect of ACE-083 on each efficacy parameter and corresponding 90% confidence intervals will be produced for the percent change data described above. For muscle strength parameters, the percent change from the screening to the baseline value will serve as the control for each cohort.

Additional analyses may be performed as appropriate.

14.2.3.2. Part 2

Primary

The primary efficacy endpoint is the percent change in total muscle volume three weeks post last dose of the double-blind treatment period from baseline, where baseline is defined as the last non-missing value prior to first dose of study drug.

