##### MRI and Muscle Strength Variables

###### Unilateral Cohorts

Individual MRI and strength data will be listed.

For each MRI and strength variable, the raw data as well as the absolute and percent change from baseline in the treated TA or BB muscle, untreated TA or BB muscle, and the treated minus untreated TA or BB muscle will be summarized for each scheduled time point.

Least square mean estimates of the effect of ACE-083 and corresponding 90% and 95% confidence intervals will be produced using an analysis of covariance (ANCOVA) for the following variables: TMV percent change from baseline 3 weeks post last dose, CCMV percent change from baseline 3 weeks post last dose, FF absolute change from baseline 3 weeks post last dose, percent change in elbow flexion MVIC 3 weeks post last dose (BB cohorts), and percent change in ankle dorsiflexion MVIC 3 weeks post last dose (TA cohorts).

The ANCOVA model will contain the following covariates:

- COHORT represents the dose level of ACE-083 administered to the muscle.
- BASELINE represents the baseline value of the parameter of interest
- BASELINE\*COHORT represents the interaction of the baseline and cohort

The analysis described above will be performed for the treated side as well as for the difference in treated and untreated sides and will be done separately for the TA and BB cohorts.

For BB patients, the above analyses will be repeated using the patient's "preferred" side used for the PUL test for patients.

Additional analyses may be performed as appropriate.

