###### Bilateral Cohort

For each MRI and strength parameter, descriptive statistics of the raw data as well as the absolute and percent change from baseline will be provided by side treated [left and right] as well as for the average of the left and right sides.

A one-sample t-test will be performed to estimate the effect of ACE-083 with corresponding 90% and 95% confidence intervals for the following variables: TMV percent change from baseline 3 weeks post last dose, CCMV percent change from baseline 3 weeks post last dose, FF absolute change from baseline 3 weeks post last dose, and percent change in ankle dorsiflexion MVIC 3 weeks post last dose.

The analysis described above will be performed using the data for the average absolute as well as the average percent change from baseline for the left and right sides.

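### Part 1: the SAP averages the screening tests into baseline and omits the protocol's screening-period control without listing the omission, so part of any pre-dose gain stays in the reported effect of ACE-083

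*SAP*

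**What the plan says.** **Protocol.** The synopsis (Statistical Analysis, Part 1) says that, for efficacy measures taken several times in the 1-month screening period, "changes observed during this time will serve as the control for each patient", and that these changes are summarized with the post-baseline data. Section 14.2.3.1 repeats the idea for strength: "the percent change from the screening to the baseline value will serve as the control for each cohort". It keeps screening and baseline separate: "Baseline is defined as the last non-missing value prior to first dose of ACE-083". The Part 1 schedule collects strength, function and FSHD-HI on Days -28, -7 and 1, so the control can be computed. Section 14.5 says that deviations from the protocol's analyses will be indicated in the SAP.

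**SAP.** For motor function, handheld strength, gait and FSHD-HI, section 4.1.4 states that "the baseline is defined as the average of the non-missing values", and adds: "Theoretically, this would be at the Screening Day -28, Screening Day -7, and Day 1 visits". The last pre-dose value is also derived and "will be available for sensitivity analyses for any analyses of changes from baseline as appropriate". MRI keeps the last-value baseline.

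The Part 1 analyses in section 4.7.2.1 are:
- Unilateral MRI and strength, by ANCOVA: "The analysis described above will be performed for the treated side as well as for the difference in treated and untreated sides".
- Bilateral cohort (3a in SAP Table 1), including ankle dorsiflexion MVIC: "A one-sample t-test will be performed to estimate the effect of ACE-083 with corresponding 90% and 95% confidence intervals".
- Motor function and FSHD-HI: ANCOVA least-squares means, presented as the drug's effect, with terms for baseline, dose cohort and their interaction.

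None of these uses the screening change. Section 5 lists the averaged baseline, and even the renaming of the safety population, but not the removal of the screening control.

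**The concern.** Strength and timed function tests depend on effort and familiarity, and FSHD-HI is self-reported. Scores may therefore drift over repeated testing with no drug given. In a part without placebo, the protocol's safeguard was to show the drift over the untreated month and to measure post-dose change from the end of it. The SAP removes both halves of that safeguard. It mixes the earliest tests into the baseline, so part of any pre-dose improvement reappears as post-dose change, and it no longer sets the screening change against the result.

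What is at stake is how the Part 1 strength results (secondary) and the motor function and FSHD-HI results (exploratory) are read. Change without a concurrent control would be reported, with confidence intervals, as an effect of ACE-083. For motor function and FSHD-HI, protocol 14.2.3.3 plans only descriptive summaries, with other analyses as appropriate. There the SAP adds effect estimates while dropping the control.

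**Working it through.** **Plan's own figures.** Part 1 has no sample-size or precision calculation to reproduce. The only design calculation is for Part 2: 12 per arm, 10% difference, SD 9%, two-sided 0.10, stated power 83%. The noncentral t with 22 df gives 83.9%, which agrees. The point does not depend on it. It matters only because 9% is the one SD in the documents, and it is for muscle volume, not strength.

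**Step 1: how much pre-dose gain stays in the post-dose change.** Take Day -28 as 0, and let a and b be the no-drug gains by Day -7 and Day 1, in the favourable direction and in percentage points. Suppose there is no drug effect and no gain after Day 1.
- Protocol baseline (last value) = b, so the post-dose change is b - b = 0.
- SAP baseline = (0 + a + b)/3, so the post-dose change is b - (a + b)/3 = (2b - a)/3.

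| Pattern of pre-dose gain | a/b | Share of b retained, (2 - a/b)/3 | If b = 6% (assumed) |
|---|---|---|---|
| All by Day -7 | 1 | 33% | 2.0 points |
| Linear in time (21 of 28 days) | 0.75 | 42% | 2.5 points |
| Equal per test | 0.5 | 50% | 3.0 points |
| All between Day -7 and Day 1 | 0 | 67% | 4.0 points |

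A pre-dose decline would push the other way. Gains after Day 1 remain under either baseline; the baseline choice cannot remove them.

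**Step 2: illustration for cohort 3a strength.** n = 6, one-sample t, 5 df, critical value 2.015, noncentrality = carried-over gain/(SD/√6). The table gives the probability that a 90% CI excludes zero with an inert drug (nominal 10%).

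| Carried-over gain | SD 5% | SD 9% | SD 15% |
|---|---|---|---|
| 2 points | 22% | 14% | 11% |
| 4 points | 52% | 25% | 15% |

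Example: 2 points at SD 9% gives noncentrality 2/(9/2.449) = 0.544 and probability 0.138. All gains, and the use of these SDs for strength, are assumptions.

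**Step 3: which estimates are exposed.** SAP Table 1 has five unilateral cohorts (1a, 2a, 1b, 2b, 3b) and one bilateral cohort (3a).
- Exposed: cohort 3a strength; the treated-side-only strength estimates; motor function and FSHD-HI in every cohort.
- Not exposed in this way: unilateral strength as treated minus untreated, which offsets gains shared by both sides; and MRI, which keeps a last-value baseline.

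**Step 4: would subtracting the screening change repair it?** With values 0, g, 2g and then flat, the SAP baseline is g, so an inert drug shows 2g - g = +g. The paired difference shows (2g - 2g) - (2g - 0) = -2g: twice the bias, in the direction that hides a benefit. With independent visit errors of equal variance σ²:
- averaged baseline: σ²(1 + 1/3) = 4σ²/3;
- last-value baseline: σ²(1 + 1) = 2σ²;
- paired difference (post - 2 × Day 1 + Day -28): σ²(1 + 4 + 1) = 6σ².

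Relative to the averaged baseline, the interval is √(6 ÷ 4/3) = 2.1 times as wide for the paired difference and √(2 ÷ 4/3) = 1.2 times as wide for the last value.

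**The case against.** The case for leaving the SAP alone has real content. Averaging three pre-dose tests is a legitimate way to cut noise with six patients per cohort, and section 5 declares it. The last pre-dose value is derived for sensitivity use. Raw data are summarized by visit, and the screening visits are mapped for tables and plots, so a reader might reconstruct the drift. The synopsis describes displaying the screening changes with later data, which falls short of a formal contrast. SAP 4.7.2.1 attaches no significance level to the bilateral t-test, so the percentages in Step 2 are not error rates of a planned decision rule. Part 1's primary objective is safety.

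These points limit the harm but do not restore the control. The sensitivity baseline is conditional, and no Part 1 analysis is committed to it. A raw-data table is not the comparator that the protocol named, and its removal is not declared.

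Two stronger readings are tempting. A reader might infer that all practice gain is counted as drug effect. Step 1 shows only part of the pre-dose gain carried over, and gains after Day 1 do not arise from averaging. A reader might also infer that the choice of muscle and dose for Part 2 rests on these estimates. Protocol 7.1 and 14.2 say that Part 1 efficacy is reviewed before Part 2, but not that the review uses this SAP's baseline or models. Decisions to enroll later cohorts rest on safety and imaging data. A gain common to all cohorts would also cancel in comparisons between dose levels.

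**Conclusion.** The point holds within limits. The SAP departs from the protocol on the Part 1 baseline and on the screening control, and declares only the first. Under the four patterns considered, 33% to 67% of any pre-dose gain stays in a change that the SAP calls the effect of ACE-083; the last-value baseline retains none. That result rests on the algebra and on the assumption that a gain occurs. Its absolute size is unknown, because the documents give neither a practice gain nor a strength SD. Over the assumed range, the effect on cohort 3a runs from almost nothing (11% against a nominal 10%) to large (52%).

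The consequence is confined to how Part 1 strength, motor function and FSHD-HI results are presented and interpreted. The documents do not support extending it to MRI, to the treated-minus-untreated strength contrast, to placebo-controlled Part 2 or to the Part 2 dose decision. A correction is worth making because it is cheap and uses data already collected.

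**What to change.** For Part 1 only, amend SAP 4.7.2.1 and section 5:

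1. For strength, motor function and FSHD-HI, report the Day -28 to Day 1 change with its 90% CI beside each post-dose change, as the protocol's screening control.
2. Commit to an analysis with the last pre-dose value as baseline, already derived under 4.1.4, alongside the averaged-baseline analysis.
3. Label the cohort 3a strength, motor function and FSHD-HI estimates as change from baseline without a concurrent control.
4. List the departure from the screening control in section 5, with the reason.

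Do not replace the estimate with post-dose change minus screening change: by Step 4 it over-corrects if gains stop at Day 1 and is about half as precise. Keep the averaged baseline in Part 2, where the placebo arm absorbs practice effects.

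The cost is SAP wording and a few small tables from data already collected. The added analysis uses a noisier single-visit baseline (interval about 1.2 times as wide under the Step 4 assumptions). The screening month is also shorter than the 3-month treatment period, so the displayed control is only a partial guide to drift over treatment.

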## Part 2 (Open-label extension)

For assessments performed in the open-label extension where data prior to the start of the open-label extension is collected at both Day 169 and 190, the baseline is defined as the mean of the assessments performed at Day 169 and Day 190. Should one of these assessments be missing, the other assessment would be used as the baseline.

For assessments performed in the open-label extension where data prior to the open-label extension is only collected at Day 190 (e.g. MRI, FSHD-HI, strength), then the baseline would be the Day 190 assessment.

### 4.1.5. Data Handling Conventions

Unless otherwise stated or indicated:

- Individual data for all patients will be presented in data listings, sorted by “Study Part” (Part 1 or Part 2), “Treatment Group”, and “Patient Number”;
- For any parameter analyzed, only observations from visits and/or time points planned in the protocol will be used in descriptive statistics. An exception to this rule is for a baseline assessment. Should an unscheduled assessment be taken after the scheduled baseline assessment but before the first dose of study medication, then the unscheduled assessment may be used as the baseline;
- For variables where the Day 1 assessment is defined as the baseline, should an individual patient have a Day 1 assessment after having received their first dose, then an unscheduled assessment may be used as the baseline, provided that the unscheduled assessment was done prior to first dose.
- For variables where the baseline is defined as the mean of Day -28, Day -7, and Day 1, should an individual patient have a Day 1 assessment taken after having received their first dose, then only the Day -28, Day -7, and any unscheduled assessment will be used to determine the average for the baseline (as described in [Section 4.1.4](#)), provided that the unscheduled assessment was done prior to first dose.
- For the determination of baseline PUL, only data on the patient’s preferred side will be used. For example, if the patient’s preferred side is “Left” and any individual PUL assessment at any of the Day -28, Day -7, and Day 1 timepoints is recorded as having been done on the “Right” or performed as “Both”, that individual assessment will not be used in the determination of the baseline PUL for that patient.
- With the exception of what is described in the preceding bullet, unscheduled assessments will not be collectively summarized in summary tables or figures; however, these data will appear in individual patient listings.
- For adverse events where the assessment of “Relationship to study drug” is missing, it will be assumed that the adverse event is “Probably Related” to study drug.
- For selected efficacy data, tests of statistical hypotheses and estimation using the end-of-treatment visit or the Day 190 visit (Part 2 double-blind component), multiple imputation for missing data will be performed. There will be no imputations performed for patients who discontinued prior to Day 43 and were replaced.

Additional techniques for handling missing data may also be considered and evaluated.

- If a patient has a Day 190 assessment performed after having received the Day 190 dose (first dose in the open-label phase), then the Day 190 assessment for that patient will be included in statistical analyses of Day 190 data only if the difference between the Day 190 assessment and the Day 190 dose date is less than or equal to 7 days.
- Descriptive statistics for quantitative parameters will be provided using number of observations (N), mean, standard deviation (SD), standard error of the mean (SEM), median, minimum and maximum;
- Should it be necessary to convert duration in days to duration in months, the duration in days will be divided by 30.417 (365/12) to calculate duration in months.
- Descriptive statistics for qualitative parameters will be provided using frequencies (N) and percentages (%).
- If the result of a continuous variable contains nonnumeric values (e.g. ‘<X’ or ‘>X’), the imputed values used for the descriptive statistics will be determined by considering the following rules:
  - If the value is ‘<X’, the value used will be X/2;
  - If the value is ‘>X’, the value used will be X.
- Concerning the determination of absolute and percent change from baseline for data such as MRI and muscle strength where assessments are reported separately for the left and right sides and the average absolute and/or percent change from baseline is needed, the absolute and/or percent change is determined for the left and right sides separately and then averaged. The “average” represents the “average” absolute (or percent) change from baseline for the left and right sides. For MRI and muscle strength data, should a patient have an MRI and/or strength assessment on one side (i.e. right side) but not the other side at an individual timepoint, the value for the average absolute (or percent) change from baseline for that patient and timepoint will be the absolute (or percent) change from the side from which the MRI and/or strength assessment was obtained.

